8.11 Exploratory Efficacy Evaluation

The efficacy analyses will be conducted on the mITT and PP populations.

8.11.1 Investigator's Global Assessment

The observed and change from Screening scores at each follow-up visit will be tabulated. For the endpoint of IGA, the treatment groups will be compared with respect to the proportions of subjects with (a) at least one-point improvement and (b) at least two-point improvement in IGA score relative to Screening at each follow-up visit using the CMH test with and without stratification on study center.

8.11.2 Acne Lesion Counts

For the endpoint of Acne Lesion Counts, the change and percent change from Screening at each follow-up visit in total, inflammatory and non-inflammatory lesions, NB01 and VEH will be compared at Visit 5/EOT using MMRM. Descriptive statistics will be provided for the observed and the change and percent change from Screening at each visit.

8.11.3 Acne QoL

For the endpoint of Acne-QoL, the change and percent change from Screening at each follow-up visit for the four domain scores separately and total, NB01 and VEH will be compared at Visit 5/EOT using MMRM. Descriptive statistics will be provided for the observed and the change and percent change from Screening at each visit.

8.11.4 Statistical / Analytical Issues

8.11.4.1 Handling of Dropouts or Missing Data

The primary method of handling missing data will be the MMRM method without explicit imputations for missing data. Since IGA is analyzed based on a “success” criteria (one- or two-point improvement in score), subjects with a missing IGA score will be considered a “failure” in the analysis for the mITT population. Analyses in the PP population will use observed data only.

8.11.4.2 Interim Analyses

No interim analyses are planned.

8.11.4.3 Multicenter Studies

Data will be pooled from the three study centers for statistical analysis. The justification for pooling is made on a clinical basis based on the following. Each center will conduct the clinical

study under a common protocol. Consistency in study execution at each center will be emphasized. The sponsor will provide monitoring of study center compliance. The results for efficacy endpoints will be presented across the three sites by treatment groups for a descriptive evaluation of treatment by site interaction.

8.11.4.4 Multiple Comparisons / Multiplicity

No multiplicity adjustment is planned in this study.

8.11.4.5 Examination of Subgroups

Subgroup analysis for IGA, lesion counts, and sebum production will be performed based on the following subgroups at Visit 5/EOT only:

- Sex: male | female
- Age: 18-25 years | 26-40 years
- Follicular engraftment success: yes | no

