- Local urine pregnancy test (Screening, Day 1, and Week 12/EOT only)
- Twice daily facial washing
- BPO pre-treatment of at least 5, but no more than 7, consecutive days (Screening). Should a subject require a modified Screening period schedule, BPO may be applied for more than 7 days with prior approval of the Sponsor Medical Monitor.
- Subject Diary completion for pre-treatment period BPO and facial washing (Screening)
- Subject Diary completion for study drug application (Day 1 through Week 12/EOT), facial washing (Day 1 through Week 12/EOT), and LSRs (Day 1 through Week 16/EOS)
- Assessment of adverse events (AEs) and local skin reactions (LSRs)
- Review of concomitant medications
- IGA (Day 1 through Week 12/EOT)
- Acne lesion counts, including inflammatory and non-inflammatory lesion counts (Day 1 through Week 12/EOT)
- Optional photography (Day 1 through Week 12/EOT)
- Sebum production measurements (Day 1 through Week 12/EOT)
- Acne Quality of Life (QoL) questionnaire (Day 1 through Week 12/EOT)
- Obtain facial samples for TaqMan® engraftment assay
 - Cheek Swab, skin surface (Day 1 through Week 12/EOT)
 - Biore® Strip, follicular (Screening, and Week 12/EOT only)
- Study drug application (Day 1 through end of Week 11*)

*Subjects must complete application of study drug at least 3 days prior to, but no more than 7 days from, the Week 12 visit.

See [Appendix 2](#) for additional details in the Schedule of Events table.

Test Product, Dose, and Mode of Administration:

NB01 is a topical live biologic. The active pharmaceutical ingredient consists of a single strain of health-associated *P. acnes* bacterium in a cryopreservative (glycerol), water and phosphate buffered saline (PBS). Vehicle-control consists of glycerol, water and PBS. Both NB01 and vehicle-control are delivered topically in single-dosed vacuum-sealed pads.

Study Measurements:

The following assessments will be completed for each subject according to the Schedule of Events (see [Appendix 2](#)).

Dosing Compliance: Measures of study drug compliance will include the duration (days) of treatment (defined as last dose date – first dose date +1), the total number of applications (determined from the doses reported in the Subject Diary), and the percent of expected doses applied. Subjects who apply at least 80% of the expected total number of applications and have no other evidence of material dosing non-compliance will be considered to be compliant with study drug dosing.

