3.3. Study Design

This is a multicenter, randomized, double-blind, vehicle-controlled Phase 1B study of daily doses of topically-delivered NB01 or vehicle-control in subjects with moderate, non-cyclical facial acne.

Subjects who consent to participate in the study will initiate Screening procedures, during which they will be pre-treated with 5% topical BPO gel once daily (QD) for 5 to 7 days before randomizing into the study. Subjects with modified screening period schedules may be able to apply BPO for more than 7 days; however, this must be pre-approved by the Sponsor’s Medical Monitor.

Thirty six subjects were randomized into the study to receive high-dose NB01 (10^5 CFU/cm²) or vehicle-control.

Subjects will be stratified according to these variables:

- Sex (male/female)
- Age (18-25 years old/26-40 years old)

The study will comprise of subjects with moderate facial acne who will be randomized to one of two treatment arms, either vehicle-control or high-dose NB01.

The study arms consist of vehicle-control control and daily high-dose (10^5 CFU/cm²) NB01, with subjects enrolled at a 2:1 ratio (treatment arm to vehicle-control arm). The PI may employ a dose reduction strategy with approval from the Sponsor's Medical Monitor to reduce/modify dosing based on individual subject's tolerability. Such changes, however, shall not be made without the written approval of the Medical Monitor, see [Section 7.4](#).

Subjects will remain on study through 11 weeks of study treatment.

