5. DEFINITIONS

- **Study Day:** The study day is the day of study relative to the first dose date and is calculated by follow-up visit date – first dose date + 1. For a subject who was randomized but not treated, the randomization date will be used.

- “Treatment success” for follicular engraftment assay: A post-Screening Follicular Biore sample having evidence of live NB01.

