8. STATISTICAL METHODS

8.1 General Considerations

All statistical processing will be performed using SAS[®] version 9.4. Summary tables (descriptive statistics and/or frequency tables) will be provided for screening and/or baseline variables, efficacy variables, and safety variables. Summaries will be provided for each treatment group. In general, continuous variables will be summarized by descriptive statistics including sample size, mean, SD, median, minimum, and maximum. Categorical variables will be summarized by frequency and percentage.

In general, all tables will be supported by relevant listing (by-subject). Figures may be created to aid in the interpretation of results.

The by visit data analyses will be summarized and analyzed using the visit window for modified intent-to-treat (mITT) and per-protocol (PP) populations based on target day as shown in Table 3.

Table 3: Analyses Windows for mITT and PP Populations

Visit	Target Day	mITT Window	PP Window
Visit 1 / Screening	-28 to -1	-28 to -1	-28 to -1
Visit 2 / Baseline	1	1	1
Visit 3 / Week 2	8	2 – 21	6 – 10
Visit 4 / Week 7	43	22 – 61	36 – 50
Visit 5 / Week 12 / EOT	80	> 61	71– 90

If there is more than one measurement within a visit after windowing is applied, the one closest to the target day will be used in the analysis by visit. If a study visit is outside of the window in PP analyses, it will be treated as missing data.

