8.2 Analysis Populations

8.2.1 *Safety Population*

The Safety population will include all randomized subjects who received and applied study drug. Subjects will have their first application of test article applied in the clinic by the PI (or sub-I-designee) during their Baseline Visit on Day 1. Subjects will be included in a treatment group based on the treatment they received (even if not the treatment group to which they were randomized). If a subject administered more than one type of test article during the trial, then the subject will be included in the treatment group to which they were randomized.

8.2.2 *Modified Intent-to-Treat Population*

The modified intent-to-treat (mITT) population will include all randomized subjects who were dispensed the study drug and have at least one post-baseline assessment. Subjects will be included in the treatment group to which they were randomized, regardless of the treatment received.

8.2.3 *Per-Protocol Population*

The per-protocol (PP) population will include a subset of the mITT population who completed the study without significant protocol deviations (as will be determined prior to unblinding the randomization) and met the criteria as specified below. Subjects will be included in the treatment group based on the treatment received.

- Meets all inclusion criteria and does not meet exclusion criteria #1-11 and #13-22.
- Has not taken or applied any interfering concomitant medications/therapies.
- Completed Visit 5/EOT procedures on Days 71 to 90 with the visit occurring 1 to 10 days after the final application of test article.
- Applied at least 80% of the expected doses with no other evidence of material dosing non-compliance.

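### Follicular engraftment success, an end-of-treatment outcome vehicle is not expected to reach, is listed as an efficacy subgroup; secondarily, no planned EOT engraftment analysis is held to the scheduled 3-7 days off drug

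*SAP*

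**What the plan says.** **Subgroup.** SAP 8.11.4.5 reads "Subgroup analysis for IGA, lesion counts, and sebum production will be performed based on the following subgroups at Visit 5/EOT only" and lists sex, age and "Follicular engraftment success: yes | no". It does not say whether arms are compared within each level, or by what method. SAP section 5 defines engraftment success as "A post-Screening Follicular Biore sample having evidence of live NB01". SAP 8.9.2 treats success at Visit 5/EOT as an endpoint compared between arms, and counts the visit as a success if any one of its samples holds live NB01. On the control product, the Protocol Synopsis says "Vehicle-control consists of glycerol, water and PBS". Protocol 3.3 gives 36 randomised subjects, allocated 2:1 to NB01 and vehicle.

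**Interval.** Footnotes p and q of the schedule of events (Protocol Appendix 2, SAP Table 1) place the EOT visit and the follicular strip 3 to 7 days after the last application, and SAP 8.8 uses the same interval. For the per-protocol (PP) population, SAP 8.2.3 requires EOT procedures on Days 71 to 90, "with the visit occurring 1 to 10 days after the final application of test article". The mITT population has no condition on time since the last dose, and its EOT window in SAP Table 3 is any day after Day 61. SAP 8.9 runs the engraftment analyses on mITT and PP only. SAP section 9 does not mention the 1-10 day criterion.

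**The concern.** A subgroup analysis keeps the protection of randomisation when the grouping variable is fixed beforehand, as sex and age are. Engraftment success is known only at EOT, the visit at which the subgroup's efficacy outcomes are read, and treatment largely decides who can reach it. If this subgroup is handled like the other two, yes may have no comparator. The no level would compare the NB01 subjects in whom the strain did not take with vehicle subjects who were never sorted that way. A reader could take the resulting display as randomised evidence that engraftment drives efficacy.

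The interval matters for a different claim: that NB01 is still present some days after application stops. A sample taken very soon after the last dose could pick up residual product, in the NB01 arm only. A late one could lower detection. Without a limit on the gap, the engraftment result cannot be tied to the interval that the schedule sets.

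**Working it through.** **1. The SAP's own figure.** SAP 8.8 derives the expected final-dose days from a Day 80 visit: 80 - 7 = 73 and 80 - 3 = 77, midpoint 75. This reproduces its Days 73-77 and its denominator of 75 doses, so the SAP itself works from the 3-7 day interval.

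**2. Cell counts.** 36 x 2/3 = 24 NB01 and 36 x 1/3 = 12 vehicle. With s NB01 successes and no vehicle positives, yes is s against 0 and no is 24 - s against 12.

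**3. Vehicle subjects in yes.** The documents give no background detection rate f, so f is assumed. The chance that yes holds no vehicle subject is (1 - f)^12.

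| Assumed f | Expected vehicle positives (12f) | Chance of none |
|---|---|---|
| 0% | 0 | 100% |
| 1% | 0.12 | 89% |
| 5% | 0.6 | 54% |
| 10% | 1.2 | 28% |

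With no vehicle subject, the stratum variance of the CMH statistic, n1·n0·m1·m0/(N²(N-1)), is zero because n0 = 0. No test exists in yes.

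**4. Bias in no.** Suppose the drug has no effect, the outcome has SD 1, and a latent tendency to engraft has correlation rho with the outcome. Let q be the NB01 success rate and c = Φ⁻¹(1 - q). The NB01 non-engrafters then differ from vehicle by rho·φ(c)/(1 - q) in size. Both rho and q are assumed.

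| q | φ(c)/(1 - q) | rho = 0 | rho = 0.1 | rho = 0.5 |
|---|---|---|---|---|
| 0.3 | 0.497 | 0 | 0.05 | 0.25 |
| 0.5 | 0.798 | 0 | 0.08 | 0.40 |
| 0.7 | 1.159 | 0 | 0.12 | 0.58 |

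If engraftable skin tends to do better anyway, the non-engrafters look worse than vehicle; a negative correlation reverses the sign. A simulation of 24 against 12 subjects with no drug effect agrees. At rho 0.5 and success rates of 25-75%, non-engrafters fall 0.22-0.63 SD below vehicle, and engrafters set against all vehicle are 0.22-0.63 SD above it. At rho 0 there is no bias.

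**5. Bias against noise.** The standard error of the no contrast is √(1/17 + 1/12) = 0.38 SD at q = 0.3 (17 non-engrafters) and √(1/7 + 1/12) = 0.48 SD at q = 0.7 (7 non-engrafters). At rho 0.5 the bias is about 0.25/0.38 = 0.7 to 0.58/0.48 = 1.2 standard errors. At rho 0.1 it is small beside the noise.

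**6. Interval.** PP admits gaps of 1 to 10 days, ten day-values. Five of them (1, 2, 8, 9 and 10) lie outside 3-7. The documents give no distribution of gaps, so the number of samples affected cannot be computed. One reclassified subject among 24 would move the NB01 success rate by 1/24 = 4.2 percentage points.

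**The case against.** The strongest reply is that SAP 8.11.4.5 never says arms will be compared within levels of engraftment success. An association display would serve a purpose that Protocol 3.7.1 states: relating biomarkers, including engraftment, to response. This stands in part. A reader might infer that within-level tests are planned, and the text does not establish that. But engraftment sits under the same instruction as sex and age with no label setting it apart, so nothing prevents the comparison either.

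A reader might also infer that the CMH test planned for IGA could look decisive on the strength of one vehicle positive. That requires a vehicle positive, every NB01 engrafter improving, and that vehicle subject not improving. Given one vehicle positive and a common improvement rate p, this table has probability p^s(1 - p). That is at most 4.9% for s = 7 and 2.1% for s = 17, so it is no basis for the point.

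On the interval, 1-10 days may be a deliberate tolerance. The PP definition in the protocol contains no off-drug interval, blinded review of deviations still applies, and having no gap rule is ordinary for an inclusive population such as mITT. All of that is fair, but it leaves the two intervals unreconciled within the SAP.

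SAP 8.1 adds "If there is more than one measurement within a visit after windowing is applied, the one closest to the target day will be used". A reader might conclude that an unscheduled strip soon after the last dose would displace the EOT strip. The documents do not establish this. SAP 6.4 places follicular sampling at Screening and Visit 5/EOT, and SAP 8.9.2 has its own rule for multiple samples. Protocol 6.2.5 and SAP Table 1 do allow strips at unscheduled visits, so their status is unclear.

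**Conclusion.** The main point holds. Follicular engraftment success is an outcome, and an analysis by it cannot be read like the sex and age subgroups. That yes will hold few or no vehicle subjects is an inference from the vehicle's composition. If arms are compared within levels, yes gives no estimate when vehicle is absent from it. In no, the contrast carries a selection bias of 0 to 0.58 SD over the assumed correlations of 0 to 0.5 and success rates of 30-70%. There is no bias if engraftability is unrelated to outcome.

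The secondary point holds in a limited form. No planned EOT engraftment analysis has a numeric rule holding it to 3-7 days off drug. It would go too far to say that the engraftment result is contaminated: the number of samples outside 3-7 days may be zero, and the net direction is unknown.

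Both points concern exploratory analyses and leave the primary safety objective unaffected.

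**What to change.** 1. Remove follicular engraftment success from the list in SAP 8.11.4.5; sex and age stay. In its place, give a descriptive EOT display of IGA, lesion counts and sebum for three groups: NB01 engrafted, NB01 not engrafted, and vehicle. Show no p-values, label the groups as formed after randomisation, and footnote any vehicle positives. This still shows how engraftment relates to response.
2. Reconcile the 1-10 day criterion in SAP 8.2.3 with the 3-7 days in SAP Table 1 and SAP 8.8, or state the reason for the difference.
3. Beside the planned analyses, add one sensitivity analysis of the EOT engraftment results only (follicular success, follicular ratios and the EOT swab), limited to EOT samples taken 3-7 days after the last application. Do not apply the limit to the Week 2 and Week 7 swabs. They are taken during daily evening dosing, about one day after the last application, and nearly all would be lost.
4. State whether a strip from an unscheduled visit can count as Visit 5.

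The cost is some SAP wording, one descriptive display and one extra analysis, using visit and last-dose dates already collected. The downside is somewhat fewer EOT samples in the added analysis.

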8.12 Safety Evaluation

All safety analyses will be performed on the Safety population.

8.12.1 *Extent of Exposure*

The study drug is supplied as single-use cotton pads. The total amount of study drug used by each subject will be calculated based on the number of days the study drug was applied (according to the subject's diary entries).

8.12.2 *Adverse Events*

All AEs reported during the study will be listed, documenting course, severity, Common Terminology Criteria for Adverse Events (CTCAE) grade, PI assessment of the relationship to the study drug, and outcome. Verbatim terms on the eCRFs will be linked to preferred terms (PTs) and system organ class (SOC) using the Medical Dictionary for Regulatory Activities (MedDRA) mapping system. For all AE summaries, if a subject has more than one AE within a preferred term, the subject is counted once in that preferred term. If a subject has more than one AE within a system organ class, the subject is similarly counted once in that system organ class.

The number and percentage of unique subjects reporting each treatment-emergent AE will be summarized by SOC and preferred term. The number and percent of unique subjects reporting each treatment-emergent AE will also be summarized by SOC, preferred term, and maximum severity (mild, moderate, severe) and closest relationship to study drug (not related, unlikely, possibly, probably, definitely).

Dose limiting toxicities, if any, will be summarized by SOC, PT and treatment group.

Serious AEs, if any, will be summarized by SOC, PT and treatment group.

For any partial date, the general rules for imputation are:

- If only day is missing, then the 1st day of the month will be used.
- If only year is present, then 01Jan will be used.

If the imputed date is for an AE start date and is in the same year and month as the first dose date but before the first dose date, then the first dose date will be used, or if the imputed AE start date is after the AE end date, then the AE end date will be used. If the imputed date is for an AE start date and is in the same year and month as, but after the last dose date + 30 days, then the last dose date + 30 days will be used.

If the imputed date is for an AE end date and is after the death date, the date of death will be used, or if the imputed AE end date is before the AE start date, the AE start date will be used.

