7.2. Adverse Event Details

AEs may be either spontaneously reported or elicited during questioning and examination of a subject. All AEs must be recorded on the AE CRF. If known, the PI should report the diagnosis of the underlying illness or disorder, rather than its individual symptoms. Subjects experiencing AEs that cause interruption or discontinuation of study drug or those experiencing AEs that are present at the end of their participation in the study should receive follow-up as appropriate. AEs should be followed to resolution or stabilization (if possible) and, if they become serious, reported as SAEs. If possible, the outcome of any AEs that caused permanent discontinuation or that were present at the end of the study, especially those considered by the PI to be related to the study drug, should be reported.

Information on the medical condition of subjects should begin following the subject’s written informed consent to participate in the study and a medical history should be taken at screening. During any wash out and baseline periods, any changes in the health of subjects should be recorded as changes in medical history unless an event occurred as a result of a study-related procedure and is unanticipated; in such cases, the event should be recorded as an AE and reported to the Institutional Review Board (IRB) as an “unanticipated problem” in accordance with local procedures. Other changes in subject health information becomes AE data when the subject begins dosing with the study drug; therefore, AE data should be collected from the date of the first dose of study drug until the date of the final study visit. These data are considered treatment-emergent AEs.

The PI will instruct the subject to report any AEs that may occur during the study. At each visit, the PI should ask the subject, in non-directive fashion, about any change in the subject’s overall

health status since the previous visit. Optional photographs may be obtained for areas outside of the face, as clinically indicated for the classification and management of AEs.

The PI will assign a CTCAE grade to all AEs (CTCAE Version 5.0, [Appendix 4](#)). The severity of each AE, as judged by the PI, will be recorded on the appropriate AE CRF and will be graded according to the following scale:

Mild - The AE is usually transient and may require only minimal treatment or therapeutic intervention. The event does not generally interfere with usual activities of daily living.

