1. INTRODUCTION

This Statistical Analysis Plan (SAP) describes the planned statistical analyses to be performed for data from Protocol NB01-P1BMA, “A Multicenter, Randomized, Double-Blind, Vehicle-Controlled Phase 1B Study of the Safety, Short-Term Engraftment and Action of NB01 in Adults with Moderate Acne”.

This SAP was created using Clinical Protocol NB01-P1BMA, Version 3.0, dated 15Jul2019, and the Electronic Case Report Forms (eCRF) Version 1.0, dated 09Nov2018.

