3.4 Primary Safety Endpoints

The safety endpoints are:

- Incidence (severity and causality) of any local and systemic AEs
- Proportion of subjects with presence (and severity) of each LSR at each time point
- Changes from Screening/Baseline to EOT in physical examination findings
- Changes from Screening/Baseline to EOT in vital signs
- Changes from Screening to EOT in CBC results

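### SAP 8.12.2 dates a year-only AE start before first dose when the AE falls in the dosing year and first dose was in February to December, so an on-treatment AE may miss the treatment-emergent tables

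*SAP*

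**What the plan says.** SAP 8.12.2 completes a partial date with the first of the month when only the day is missing. When more is missing: "If only year is present, then 01Jan will be used".

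A guard then protects on-treatment starts. It opens "If the imputed date is for an AE start date and is in the same year and month as the first dose date" and, where the imputed date is earlier than first dose, substitutes the first dose date. Two further clauses adjust a start: one sets it to the AE end date if it falls after that, the other caps it at 30 days after last dose.

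On the tables, the same section says "The number and percentage of unique subjects reporting each treatment-emergent AE will be summarized by SOC and preferred term". The severity and relationship tables carry the same restriction. The AE listing and the summaries of serious AEs and dose-limiting toxicities do not.

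The SAP does not define treatment-emergent. Protocol 7.2 says "AE data should be collected from the date of the first dose of study drug until the date of the final study visit", and then "These data are considered treatment-emergent AEs". Protocol 8.4.2 says that all reported AEs are summarized and names no such restriction. SAP 3.4 lists among the primary safety endpoints "Incidence (severity and causality) of any local and systemic AEs".

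**The concern.** The guard exists so that an AE with an uncertain start is not placed before dosing by the imputation itself. It works when the month is known. It fails for the less complete year-only date, because the imputed month is always January and the guard demands the month of first dose. It can therefore act on a year-only start only after a January first dose.

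At stake is the incidence of treatment-emergent AEs, part of the primary safety evaluation in a 36-subject trial. For AEs that truly began on treatment the error has one direction: they are left out. It acts on both arms alike.

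**Working it through.** The plan gives no figure to reproduce. The check applies the rule literally.

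**1. Can another clause rescue a 01Jan date?** No. The end-date clause and the cap of last dose plus 30 days can only move a start earlier.

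**2. Single cases (year-only start).**

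| First dose | AE year | Imputed start | Relative to first dose |
|---|---|---|---|
| 15Jan2019 | 2019 | 15Jan2019 (guard acts) | same day |
| 01Feb2019 | 2019 | 01Jan2019 | 31 days before |
| 15Mar2019 | 2019 | 01Jan2019 | 73 days before |
| 10Jul2019 | 2019 | 01Jan2019 | 190 days before |
| 20Nov2019 | 2020 | 01Jan2020 | 42 days after |

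The last row is the exception: an AE in the calendar year after first dose is kept. With follow-up to Day 106 (Protocol 6.2.4) this can arise only for first doses after about 17 September.

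**3. Share misdated, given a year-only start.** Cross every first dose date with every onset on Days 1 to 106, equally weighted. Share = (pairs with imputed start before first dose) / (dates × 106).

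The enrolment window is an assumption. The SAP introduction cites protocol "Version 3.0, dated 15Jul2019, and the Electronic Case Report Forms (eCRF) Version 1.0, dated 09Nov2018". Protocol 3.3 says "Thirty six subjects were randomized into the study to receive high-dose NB01", so I took first doses to lie between those two dates.

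- 09Nov2018 to 15Jul2019: 249 × 106 = 26,394 pairs. Misdated by month of first dose: November 935 of 2,332, December 496 of 3,286, January 0 of 3,286, February to July 17,490 of 17,490. Total 935 + 496 + 0 + 17,490 = 18,921, or 71.7%.
- First doses from 01Jan2019: 17,490 / 20,776 = 84.2%. From 01Feb2019: 17,490 / 17,490 = 100%.
- All twelve 8-month windows (a one-year study less about four months per subject): 65.5% to 99.6%.
- A full calendar year: 29,839 / 38,690 = 77.1%.

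These are shares of a probably rare event, not effects on the trial result.

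**4. Month recorded.** With a complete end date, no start is misdated. With only the month recorded for both start and end, the outcome depends on whether the start-after-end clause uses the imputed end date, which the SAP does not say. If it does, 15,261 of 193,450 cases (7.9%) are pulled before first dose (365 dates × 106 onsets × AE durations of 1, 3, 7, 14 and 28 days).

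**5. The opposite error.** On the inferred window there are 249 × 14 = 3,486 pairs with onset on Days -14 to -1. With a year-only start, the current rule makes 329 of them (9.4%) treatment-emergent. They belong to January first doses, where the guard moves a January screening onset to the first dose date.

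**6. Effect on one row.** Assuming the 2:1 ratio gave exactly 24 and 12 subjects, losing a subject's only event in a row lowers it by 1/24 = 4.2 points (NB01) or 1/12 = 8.3 points (vehicle).

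**The case against.** The strongest objection is that loss from the tables is inferred. Protocol 7.2 describes treatment-emergent AEs by when the data are collected, and pre-dose events mostly go to medical history. An AE first reported at a post-dose visit could be flagged without using its imputed date. This stands as a condition on the conclusion. It does not remove the problem: serious and procedure-related AEs from screening also go on the AE form (Protocol 6.2.1), so something must separate them, and a first-dose guard has little purpose unless dates are compared.

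Second, year-only starts should be rare. Contacts are planned on Days 8, 43, 80 and 106, so gaps are at most 37 days, subjects are asked about changes since the previous visit, and data are monitored before the freeze. Nothing in the documents shows that such a start exists. This stands, and it keeps the point minor.

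Third, Protocol 8.4.2 summarizes all reported AEs. That would protect the count if the tables followed it, but the SAP's SOC and preferred-term tables are limited to treatment-emergent AEs and SAP section 9 lists no change on this. The two texts need aligning.

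A reader might also infer that every year-only AE after a February to December first dose is lost, or that the rule can only lower incidence. Neither is supported: AEs in the following calendar year are kept, and after a January first dose the guard can add a screening onset.

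**Conclusion.** The rule as written gives the wrong side of first dose for a defined set of cases: AE start known only by year, that year being the year of first dose, first dose in February to December. Within that set, every on-treatment AE is dated before first dose.

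Exclusion from the SOC and preferred-term, severity and relationship tables follows if the flag compares imputed start with first dose. The documents point that way without saying so; they do not support stating the loss as certain.

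The conditional shares in the working rest on assumed enrolment windows and equally weighted dates and onsets. How many AEs will be affected is unknown and probably very small. AE listings keep every event, the serious AE and dose-limiting toxicity summaries are not restricted to treatment-emergent AEs, and the local skin reaction tables do not use AE dates. This is a minor defect, worth correcting because it touches a primary safety endpoint and costs little.

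**What to change.** Make two edits to SAP 8.12.2 before the initial data freeze described in SAP 8.3, when the project statistician is unblinded.

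1. State that an AE is treatment-emergent if its start is on or after first dose, citing Protocol 7.2, and say how the tables relate to the all-AE summary in Protocol 8.4.2.
2. Replace the first-dose guard with: *If the recorded parts of a partial AE start date (year, or year and month) match those of the first dose date, use the first dose date, unless the recorded parts of the AE end date show that the AE ended before first dose. Imputed end dates are not used for this check or for the start-after-end clause, for any partial start date.*

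Under this rule no on-treatment onset is dated before first dose: 0 of 26,394 on the inferred window, 0 of 38,690 on the calendar year, and 0 of 193,450 in the end-date test, whether the end is complete, lacks the day or gives only the year. The last sentence of the new text closes the 7.9% gap.

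The cost is a short text change and a few lines of code. The downside is that year-only screening onsets with no recorded earlier end would mostly count as treatment-emergent: 3,381 of 3,486 (97.0%) on the inferred window, against 329 now. Only screening serious AEs and procedure-related AEs can be affected, so the number should be very small, and over-counting is the conservative direction for safety. SAP 8.12.8 borrows the AE date rules for medications and should say whether the new guard applies there.
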